#### **5.3** Criteria to Resume Treatment

Patients may resume treatment with study drug when the drug-related AE(s) resolve to Grade ≤1 or baseline value, with the following exceptions:

- Patients may resume treatment in the presence of Grade 2 fatigue;
- Patients who have not experienced a Grade 3 drug-related skin AE may resume treatment in the presence of Grade 2 skin toxicity;
- Patients with baseline Grade 1 AST/ALT or total bilirubin who require dose delays for reasons other than a 2-grade shift in AST/ALT or total bilirubin may resume treatment in the presence of Grade 2 AST/ALT or total bilirubin;
- Patients with combined Grade 2 AST/ALT and total bilirubin values meeting discontinuation parameters should have treatment permanently discontinued;
- Drug-related pulmonary toxicity, diarrhea, or colitis, must have resolved to baseline (Grade 1) before treatment is resumed. Patients with persistent Grade 1 pneumonitis after completion of a steroid taper over at least 1 month may be eligible for retreatment following discussion with the Study Chair or Co-Chair;
- Patients with drug-related endocrinopathies adequately controlled with only physiologic hormone replacement may resume treatment following discussion with the Study Chair or Co-Chair.

If the criteria to resume treatment are met, the patient should restart treatment at the next scheduled time point as per protocol. However, if the treatment is delayed past the next scheduled time point as per protocol, this time point should become day one of the subsequent cycle. If treatment is delayed or interrupted for > 6 weeks, the patient must be permanently discontinued from protocol therapy.

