## 6.2 Dose Modifications for Non-Haematological Toxicity

Patients who have any Grade 3 or Grade 4 non-hematological toxicity attributable to the investigational drug with the specific exclusion of the following, will be removed from the study:

- Grade 3 ALT that returns to levels that meet initial eligibility criteria or baseline within seven (7) days and does not require systemic immunosuppression;
- Grade 3 liver enzyme elevation, including AST/GGT that returns to baseline within 7 days and does not require systemic immunosuppression;
- Grade 3 or 4 serum electrolyte or mineral abnormalities responsive to supplementation;
- Grade 3 or 4 amylase or lipase abnormalities that are not associated with diabetes mellitus (DM), associated liver or gall bladder inflammation or clinical manifestations of pancreatitis;
- isolated Grade 4 amylase or lipase abnormalities that are not associated with symptoms or clinical manifestations of pancreatitis and decrease to < Grade 4 within 1 week of onset;
- Grade 3 rash/oral lesions that resolves to Grade  $\leq 1$  within seven (7) days;
- Grade 3 or 4 seizures (multiple seizures despite medical intervention or life-threatening seizures/status epilepticus) that may occur in the context of pseudo-progression;
- fever greater than 40°C of ≤24 hr. duration;
- Grade 3 fatigue that resolves to Grade  $\leq 2$  within 7 days;
- Grade 3 creatinine increase that resolves to Grade  $\leq 1$  or baseline within seven (7) days.

Patients who experience the following non-hematological toxicities attributable to protocol therapy will also be removed from the study:

- Grade 2 fever that does not resolve to Grade  $\leq 1$  within seven (7) days;
- Grade 2 uveitis, eye pain or blurred vision that does not respond to topical therapy and does not improve to Grade 1 prior to next scheduled dose;
- Grade 2 non-hematological toxicity requiring systemic immunosuppressive therapy. This includes, but is not limited to, autoimmunity of the lung, heart, kidney, bowel, CNS, pituitary or eye;
- Grade 2 endocrine toxicity requiring hormone replacement, with the exception of Grade
   2 hypothyroidism, thyroiditis and thyroid dysfunction adequately managed with thyroid hormone replacement;
- Grade 2 adrenal insufficiency;
- Grade 3 colitis or Grade 3 diarrhea attributable to protocol therapy of more the seven (7) days of duration.

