## **6.9** Dose Modifications for Neurologic Adverse Events

Neurologic events	Management/Next Dose of Nivolumab					
≤ Grade 1	Continue protocol therapy.*					
Grade 2	Hold until resolution to baseline.* Resume with no change in dose.*					
Grade 3	Off protocol therapy.					
Grade 4	Off protocol therapy.					

\*Patients with any CNS events including aseptic meningitis, encephalitis, symptomatic hypophysitis, or myopathy, peripheral demyelinating neuropathy, cranial neuropathy (other than peripheral n. VII), GB syndrome, myasthenia gravis should be taken off protocol therapy.

**Recommended management:** See Neurologic Adverse Event Management Algorithm below (see *Section 6.9.1*).

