#### **6.11 Dose Modifications for Endocrine Adverse Events**

Endocrine	Management/Next Dose of Nivolumab				
Hypophysitis; Adrenal					
Insufficiency					
≤Grade 1	Continue protocol therapy.				
Grade 2	• Off protocol therapy, unless exception in Section 6.2 is met				
	(Grade 2 hypothyroidism, thyroiditis and thyroid dysfunction				
	adequately managed with thyroid hormone replacement).				
Grade 3	Off protocol therapy.				
Grade 4	Off protocol therapy.				

Note: All patients with symptomatic pituitary enlargement, exclusive of hormone deficiency, but including severe headache or enlarged pituitary on MRI should be considered Grade 3 events. Isolated thyroid or testosterone deficiency may be treated as Grade 2, if there are no other associated deficiencies and adrenal function is monitored.

Please evaluate pituitary function before beginning steroid therapy or replacement therapy of any kind.

Recommended management: See Endocrine AE Management Algorithm (see Section 6.11.1).

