\* For symptomatic hypothyroidism, nivolumab should be withheld, and thyroid hormone replacement should be initiated as needed. For symptomatic hyperthyroidism, nivolumab should be withheld and methimazole should be initiated as needed. Corticosteroids at a dose of 1 to 2 mg/kg/day methylprednisolone equivalents should also be considered if acute inflammation of the thyroid is suspected. Upon improvement, nivolumab may be resumed after corticosteroid taper, if needed. Monitoring of thyroid function should continue to ensure appropriate hormone replacement is utilized.

For symptomatic **adrenal insufficiency**, nivolumab should be withheld, and physiologic corticosteroid replacement should be initiated as needed. Monitoring of adrenal function and hormone levels should continue to ensure appropriate corticosteroid replacement is utilized.

For symptomatic **hypophysitis**, Nivolumab should be withheld, and hormone replacement should be initiated as needed. Corticosteroids at a dose of 1 to 2 mg/kg/day methylprednisolone equivalents should also be considered if acute inflammation of the pituitary gland is suspected. Upon improvement, Nivolumab may be resumed after corticosteroid taper, if needed. Monitoring of pituitary function and hormone levels should continue to ensure appropriate hormone replacement is utilized.

For symptomatic **diabetes**, nivolumab should be withheld, and insulin replacement should be initiated as needed. Monitoring of blood sugar should continue to ensure appropriate insulin replacement is used.

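### Symptomatic hypophysitis is taken off nivolumab in 6.9 and 6.11 but may be re-treated under the 6.11.1 footnote; Grade 2 adrenal insufficiency has a similar, less direct conflict

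*Protocol*

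**What the plan says.** **Text that ends treatment**

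- Section 6.9, footnote to the dose table: "Patients with any CNS events including aseptic meningitis, encephalitis, symptomatic hypophysitis, or myopathy", among other listed events, are to come off protocol therapy. No grade is given. The footnote's asterisk is attached to the rows that otherwise continue or hold treatment (Grade 1 or lower, and Grade 2).
- Section 6.11, table headed for hypophysitis and adrenal insufficiency: off protocol therapy at Grades 2, 3 and 4. The only exception, at Grade 2, is for thyroid conditions managed with thyroid hormone. A note adds that symptomatic pituitary enlargement, exclusive of hormone deficiency, "should be considered Grade 3 events".
- Section 6.2: "Patients who experience the following non-hematological toxicities attributable to protocol therapy will also be removed from the study". The list that follows includes "Grade 2 adrenal insufficiency" without qualification, "Grade 2 endocrine toxicity requiring hormone replacement" (thyroid conditions excepted) and "Grade 2 non-hematological toxicity requiring systemic immunosuppressive therapy", where the pituitary is one of the named examples.

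**Text that allows treatment to resume**

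- Section 6.11.1, footnote paragraph on symptomatic hypophysitis: withhold, replace hormones, consider corticosteroids, and then "Upon improvement, nivolumab may be resumed after corticosteroid taper, if needed". The sentence stands in both the thyroid and the hypophysitis paragraphs; in the latter the drug name has a capital letter.
- Section 6.11.1, table row for symptomatic endocrinopathy: hold, treat and, if the patient improves with or without hormone replacement, taper steroids and resume per protocol. The same follow-up list says that adrenal-insufficiency patients may need to stay on steroids.
- Section 5.3: "Patients with drug-related endocrinopathies adequately controlled with only physiologic hormone replacement may resume treatment", subject to discussion with the Study Chair or Co-Chair. It is not limited to thyroid disease.

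**The concern.** An investigator whose patient has recovered from symptomatic hypophysitis finds one section that ends nivolumab and another that permits it again. Both are in force, and 6.11 sends the reader to 6.11.1 for management.

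Safety and tolerability is a secondary objective (Section 2.2). Treatment exposure and the number of patients who stop for toxicity are basic descriptions of tolerability. If the same event can count as a permanent discontinuation or as a dose delay, those summaries partly reflect which section was applied. Re-exposure of a child after pituitary or adrenal injury is also a safety matter that the protocol should settle in one way.

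**Working it through.** The protocol states no figure on this point that could be reproduced. The check is a comparison of the rules for one and the same event.

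| Event | Ends treatment | Allows resumption |
|---|---|---|
| Symptomatic hypophysitis, improved after steroid taper | 6.9 footnote (no grade limit); 6.11 table (Grade 2 and above) | 6.11.1 footnote (no qualifier); 5.3 if on physiologic replacement only, after discussion with the Chair |
| Grade 2 adrenal insufficiency, controlled on replacement | 6.2 (named); 6.11 table | 5.3 (after discussion with the Chair); 6.11.1 table (per protocol) |

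**Hypophysitis.** The event is named in 6.9, in the heading of the 6.11 table and in the 6.11.1 footnote, so no interpretation is needed to see that all three apply. The thyroid exception in 6.2 and 6.11 does not reach it. Section 6.2 does not use the word, but it reaches Grade 2 cases that need hormone replacement or systemic immunosuppression. The 6.11.1 row itself prescribes methylprednisolone for symptomatic disease with abnormal laboratory or scan findings. The 6.11.1 hypophysitis sentence carries no reference back to 6.2, 6.9 or 6.11.

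**Adrenal insufficiency.** Section 6.2 names it and 6.11 repeats removal. On the other side the text is less direct. The adrenal paragraph of the 6.11.1 footnote says to withhold and replace, and says nothing about resuming. Resumption comes from the general wording of 5.3 and from the 6.11.1 table, where it is qualified as per protocol.

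**Timing.** Section 6.2 also removes a patient for any non-haematological toxicity that delays therapy by more than 7 days. Section 6.11.1 asks for a taper of at least 1 month before resumption, and 5.3 sets the limit at more than 6 weeks. One month exceeds 7 days, so under 6.2 a resumption after that taper could not be reached; under 5.3 it could.

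**Does another section settle it?** Section 13.2 refers to Section 7 for adverse events that require removal. Section 7.13 names hypophysitis but only advises evaluation, monitoring and consultation. Section 7.10 states removal for Grade 3 or greater hypothyroidism. Section 7.14, on other immune-mediated events, allows resumption after a taper. None gives a rule that decides between 6.9 or 6.11 and 6.11.1.

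**Scale.** Section 1.6.3 lists hypophysitis among the most common drug-related immune events in the adult phase I study of nivolumab, but gives no rate. For scale only, assume an incidence of 1% to 5% among the 50 planned patients: 0.01 × 50 = 0.5 and 0.05 × 50 = 2.5 patients.

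**The case against.** The best defence is that the protocol contains a hierarchy. Sections 5.1 and 5.2 allow further dosing only if no criterion for removal has been met, and the note under 5.2 sends patients who need a delay to 5.3. On that reading 5.3 serves only patients who have not met a removal criterion, such as the thyroid cases excepted in 6.2. Section 6.11.1 is titled as a recommendation, and its table ties resumption to the protocol. Divergence between sites is also restrained: 5.3 requires discussion with the Study Chair or Co-Chair, Section 6 requires that dosage modifications be notified to them, and the 8.2 calendar notes ask for delays to be discussed beforehand.

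Much of this stands. It weakens the 5.3 argument and makes the adrenal conflict an ambiguity rather than a flat contradiction. It does not remove the hypophysitis conflict. The protocol does not say that 5.2 subordinates 5.3 or 6.11.1 for these events, and the hypophysitis sentence has no such qualifier. If the removal rules do govern, that sentence has no effect from Grade 2 upward and misleads whoever reads it.

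Four stronger readings are tempting but not supported:

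- That diabetes is affected in the same way. The 6.11.1 paragraph on diabetes says to withhold and give insulin, with no instruction to resume, so it does not contradict removal.
- That 6.9 also removes adrenal insufficiency. It does not mention it.
- That sites will certainly act differently. The Chair's involvement makes this a possibility, not a certainty.
- That the efficacy results are materially distorted. PFS is defined to progression or death, not to the end of treatment, and Section 10.4.1 lets assessments after discontinuation count towards best response.

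**Conclusion.** The contradiction for symptomatic hypophysitis is in the text: off therapy under 6.9 and, from Grade 2, under 6.11; eligible to resume under 6.11.1. The conflict for Grade 2 adrenal insufficiency controlled on replacement is secondary. It depends on reading 5.3 and the 6.11.1 table as independent of the removal criteria, which the protocol neither states nor rules out.

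What can change is exposure, the count of discontinuations for toxicity and the safety of re-treatment. The effect on ORR and PFS is probably small. The number of patients cannot be derived from the documents; the 0.5 to 2.5 shown above rests wholly on an assumed incidence, and the conclusion does not depend on it. No view is taken on which clinical rule is right.

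**What to change.** Reconcile 5.3, 6.2, 6.9, 6.11 and 6.11.1. Hypophysitis and adrenal insufficiency should each have one instruction by grade (hold, resume or remove), in the same words wherever it appears. The reconciled text should cover three details:

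- whether the 6.9 footnote applies at every grade, since 6.11 continues therapy at Grade 1 or lower;
- whether the general resumption item in 5.3 and the resume line in 6.11.1 extend to events that 6.2 lists for removal;
- how the 7-day limit in 6.2, the 6-week limit in 5.3 and the taper of at least 1 month in 6.11.1 fit together.

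Add one sentence stating which section governs if they differ. The sponsor decides the clinical rule. The cost is a wording amendment with the usual approvals; no added tests, visits or patients are needed.

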#### **6.12 Dose Modification for Fever**

Fever	Management/Next Dose of Nivolumab
(CTCAE v.4.03)	
Grade 1	Continue protocol therapy
Grade 2	
 
Hold until ≤ Grade 1. If resolves to ≤ Grade 1 within seven (7) days, resume at same dose level. If fever does not resolve to ≤ Grade 1 within seven (7) days, discontinue protocol therapy.
 

Grade 3	
 
Hold until ≤ Grade 1. If resolves to ≤ Grade 1 within 24 hours, resume at same dose level. If fever does not resolve to ≤ Grade 1 within 24 hours, discontinue protocol therapy.
 

Grade 4	Off protocol therapy

Patients with fever should be evaluated as clinically appropriate. Patients may experience isolated fever during infusion reactions or up to several days after infusion. Evaluation over the course of 1-2 weeks should be done for other autoimmune events that may present as fever

#### **6.13** Dose Modifications for Renal Adverse Events

Refer to algorithm below for dose modifications for renal adverse events and recommended management guidelines.

## 6.13.1 Recommended Renal Adverse Event Management Algorithm

Toxicity (CTCAE v.4)	Management	Follow-up
Grade 1 Creatinine > ULN and > than baseline but ≤ 1.5 x baseline.	
 
Continue protocol therapy;
 
Monitor creatinine weekly
 
	If returns to baseline: Resume routine creatinine monitoring per protocol.  If worsens: Treat as Grade 2 or 3/4
Grade 2 or 3 Creatinine > 1.5 x baseline to $\leq$ 6x ULN	
 
Delay nivolumab per protocol;
 
Monitor creatinine every 2-3 days;
 
0.5-1.0 mg/kg/day methylprednisolone IV or oral equivalent;
 
Consider renal biopsy and consult nephrology.
 
	
 
If returns to Grade 1 or baseline:
 
Taper steroids over at least 1 month
 
Consider prophylactic antibiotics for opportunistic infections;
 
Resume nivolumab as per protocol
 
Routine creatinine monitoring as per protocol.
 
If elevations persists > 7 days or worsen:
 
Treat as Grade 4.
 

Grade 4 Creatinine > 6x ULN	
 
Discontinue protocol therapy;
 
Monitor creatinine daily;
 
1.0 - 2.0 mg/kg/day methylprednisolone IV or IV equivalent;
 
Consult nephrologist;
 
Consider renal biopsy.
 
	If returns to Grade 1:  • Taper steroids over at least 1 month and add prophylactic antibiotics for opportunistic infections.

Patients on IV steroids may be switched to an equivalent dose of oral corticosteroids (e.g. prednisone) at start of tapering or earlier, once sustained clinical improvement is observed. Lower bioavailability of oral corticosteroids should be considered when switching to the equivalent dose of oral corticosteroids.

## 7. SUPPORTIVE CARE AND OTHER CONCOMITANT THERAPY

## 7.1 Concurrent Anti-Cancer Therapy

Concurrent anti-cancer therapy, including chemotherapy, radiation therapy, immunotherapy, or biologic therapy may NOT be administered to patients receiving study drug. If these treatments are administered the patient will be removed from protocol therapy.

## 7.2 Investigational Agents

No other investigational agents may be given while the patient is on study.

## 7.3 Supportive Care

Appropriate antibiotics, blood products, anti-emetics, fluids, electrolytes and general supportive care are to be used as necessary. Specific supportive care measures for management of autoimmune reactions are detailed below (see throughout *Sections 7.4-7.8* and all of *Section 7.9*):

## 7.4 Skin Related Toxicity

For skin-related Grade 3 autoimmune toxicity lasting > 7 days or Grade 4 autoimmune toxicity, including severe generalized pruritus or rash, symptomatic treatment will be given, and patients will be removed from protocol therapy. Therapy will be as clinically indicated and may include local skin care, antihistamines, or corticosteroids (which can be local/topical or systemic). The use of topical corticosteroids for grades 1-3 dermatitis will be allowed, and will not require patients to be removed from study. In the case of late-occurring hypersensitivity symptoms (e.g., appearance within one week after treatment of a localized or generalized pruritus), symptomatic treatment may be given (e.g., oral antihistamine, topical steroids for the skin).

A dermatologist should evaluate persistent (lasting greater than seven (7) days) and/or severe rashes or pruritus. Patients should be advised to seek medical evaluation if they notice new-onset rash. Early consultation with a dermatology specialist and a biopsy should be considered if there is uncertainty as to the cause of the rash, or if there is any unusual appearance or clinical feature associated with it. Other drugs that may cause rash should be considered in the differential and, if possible, discontinued. A biopsy should be performed if appropriate and photos should be obtained.

If symptoms or signs of SJS or TEN appear, nivolumab should be withheld and the patient should be referred for specialized care for assessment and treatment. If the patient has confirmed SJS or TEN, permanent discontinuation of nivolumab is mandatory.

Please refer to *Sections 6.4 and 6.4.1* for dose modification and management of the skin toxicities.

#### 7.5 Pneumonitis

Early recognition and treatment of pneumonitis is critical to its management. Patients should be advised to seek medical evaluation promptly if they develop new-onset dyspnea, cough, or fever or if they have worsening of these baseline symptoms. It is important that an evaluation/work-up distinguishes between non-drug-related causes (e.g., infection or progression of disease) and a possible drug-related pulmonary toxicity as the management of these events can be quite different. For symptomatic nivolumab-related pneumonitis, the principal treatment is corticosteroids. Refer to *Section 6.7.1* for recommended pulmonary adverse event management algorithm.

Grade 1 asymptomatic patients with radiological changes (e.g., focal ground glass opacities and patchy infiltrates) may be managed with nivolumab dose delay. Patients with Grade 2 pneumonitis or with symptoms of dyspnea, cough, or fever should be managed with dose delay, and treatment with corticosteroids should be considered. Nivolumab can be resumed at the same dose after the resolution of the symptoms and radiographic changes, cessation of corticosteroid therapy and after pulmonary and/or ID consultation if lymphocytic pneumonitis is excluded. Note, that in cases where nivolumab treatment was restarted, recurrence of pneumonitis was reported infrequently. All patients with Grade 3-4 pneumonitis (with more extensive radiographic findings, and hypoxia) should permanently discontinue nivolumab and treat with high-dose corticosteroids. Patients with more severe cases of pneumonitis, who did not initially respond to corticosteroids, can be treated with addition of immunosuppressive therapy (infliximab, cyclophosphamide, IVIG, or mycophenolate mofetil) as per discretion of the treating physician.

#### 7.6 Ocular Toxicity

Patients who report any new visual symptom, ocular findings on exam, or change in vision should be immediately referred to an ophthalmologist. Ophthalmologic evaluation should include

but will not be limited to examination of the conjunctiva, anterior and posterior chambers and retina, normal and dilated slit-lamp examination. The patient will be treated as deemed appropriate by the ophthalmologist, including peri-ocular steroid injections or steroid eye drops if necessary to manage low-grade events. High-grade events should be managed with systemic corticosteroids. Complaints of double vision should also prompt medical evaluation. In addition to ocular inflammatory events, a work-up should also consider pituitary inflammation as a cause. Vogt-Koyanagi-Harada syndrome (VKH) is a T-cell mediated autoimmune attack on melanocytes that should be ruled out. VKH manifests as a multi-system disorder characterized by granulomatous panuveitis with exudative retinal detachments, often associated with neurologic and cutaneous manifestations. Based on the severity of such a syndrome, nivolumab treatment should be withheld or discontinued, and corticosteroids administered accordingly.

